#### 17.3 Statistical Analysis:

**Stigma Quantification:** Each of the four SP scenarios will be coded across two binary variables ("MSM" and "HIV") that will separately account for whether same-sex behaviors, HIV+ status, or both were announced by the SP during the provider visit. The scenarios will then be regressed on the quality of care index to assess the excess erosion of care observed in visits where SPs present as both HIV infected and as MSM, beyond the simple sum or product of the erosion experienced with only one of the attributes. Specifically, we will estimate:

$$\theta_{ijs} = \alpha + \beta_1 HIV_{ij} + \beta_2 MSM_{ij} + \beta_3 (HIV_{ij} * MSM_{ij}) + \gamma_j + \eta_s + \varepsilon_{ijs}$$

where  $\theta_{ijs}$  is the quality of care index as measured in SP interaction  $i$  in facility  $j$  conducted by SPs;  $HIV_{ij}$  is an indicator for the HIV status of the SP scenario in that given provider encounter;  $MSM_{ij}$  an indicator for the MSM status of the SP scenario in that given provider encounter;  $\gamma_j$  is a vector of facility fixed effects; and  $\eta_s$  is a vector of fixed effects for SPs. Here,  $\beta_1$  and  $\beta_2$  provides an estimate of HIV and

PROTOCOL TITLE: Standardized Patients to Address Intersectional Stigma  
 VERSION DATE: 07/23/2019

MSM stigma respectively, and  $\beta_3$  the estimate of stigma due to the presence of both HIV and MSM status.

Preliminary intervention effects: We will estimate the main intention-to-treat (ITT) impact of the training intervention using the Ordinary Least Squares (OLS) regression:

$$\theta_{idc} = \beta_0 + \beta_1 T_c + \beta_2 \bar{\theta}_{dc(t-1)} + \gamma X_{ic} + \varepsilon_{idc}$$

where  $\theta_{ict}$  is the healthcare quality index from SP interaction  $i$  with doctor  $d$  in clinic  $c$  measured at follow-up,  $T_c$  is a dummy variable that takes the value of 1 if the clinic was randomized to be offered training and 0 if in the control group. The coefficient of interest is  $\beta_1$ , which captures the ITT effect of training on the quality of care. We control for the average quality index from all SP interaction with doctor  $d$  at baseline,  $\bar{\theta}_{dc(t-1)}$ , as well as a vector of SP and disease script type (varying HIV and MSM status) fixed effects.  $\varepsilon_{idc}$  represents the idiosyncratic error, which we cluster at the clinic, the level of randomization.

The ITT impacts reflect the effect of physicians being *offered* an opportunity to participate in training, not the causal effect of training itself. We therefore also estimate the effect of participating in training using the model

$$\theta_{idc} = \pi_0 + \pi_1 A_{dc} + \pi_2 \bar{\theta}_{dc(t-1)} + \varphi X_{ic} + \nu_{idc}$$

where  $A_{dc}$  is a measure of whether or not doctor  $d$  in clinic  $c$  attends the training and other variables are defined as above. We fit this equation by two-stage least squares (2sls) using the following first-stage equation:

$$A_{dc} = \delta_0 + \delta_1 T_c + \delta_2 \bar{\theta}_{dc(t-1)} + \zeta X_{ic} + \mu_{idc}$$

where the excluded instrument is the treatment assignment of doctor  $d$ 's clinic,  $T_c$ . We interpret the coefficient  $\pi_1$  as the local average treatment effect, or LATE, of participating in training on the quality of care provided.

While the analysis outlined above provides estimates of the effect of the training (or offer of training) on the quality of care provided to SPs presenting with cases of presumptive syphilis, the goal is to estimate the effect of the training on *enacted stigma*. That is, rather than the overall effect on the level of healthcare quality, we are primarily concerned with observing how the training affects the difference in the quality of care received by patients presenting as MSM or HIV-positive vs. those not, all else equal. Our two levels of randomization (SP-doctor interactions disease script types and clinics to treatment or control) allow us to estimate the causal effect of training offer (or participation) by estimating regressions analogous to the above, but interacting the dummy clinic treatment allocation with dummy variables for each SP script type. For ITT effects, we estimate

$$\theta_{idc} = \alpha_0 + \alpha_1 T_c + \alpha_{11} T_c \times V^{HIV+,MSM-} + \alpha_{12} T_c \times V^{HIV-,MSM+} + \alpha_{13} T_c \times V^{HIV+,MSM+} + \alpha_2 \bar{\theta}_{dc(t-1)} + \gamma \Gamma_{ic} + \varepsilon_{idc}$$

Where  $V$  are dummy variables for three of the four script variations (leaving out the HIV-, MSM- variation).  $\Gamma_{ic}$  is a vector of SP fixed effects. The coefficients  $\alpha_{11}$ – $\alpha_{13}$  represent the effect of training offer on the *difference* in healthcare quality provided

PROTOCOL TITLE: Standardized Patients to Address Intersectional Stigma  
VERSION DATE: 07/23/2019

to SPs presenting as {HIV+,MSM-}, {HIV-,MSM+}, and {HIV+,MSM+} compared to {HIV-,MSM-}.

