## **17.0 Data Management**

### **17.1 Data Analysis Plan:**

The primary goal of the study is to estimate the impact of healthcare stigma—in particular stigma directed at patients living with HIV (HIV stigma), patients who have same sex behaviors (homophobia), and patients with both attributes (intersectional stigma) on the quality of sexual healthcare they receive. Stigma is quantified as the difference in the mean healthcare quality index across the four case scenarios. Patterns of stigma occurrence are also assessed by stratifying results across key attributes such as tier of care (e.g. county hospital versus township clinic), rural/urban region, provider sex, and provider professional rank in order to illuminate provider subgroups of interest to inform tailored intervention design. A secondary analytical goal of this study is to assess the preliminary effect of the intervention on healthcare quality by comparing the same healthcare quality index across treatment arms. Details in the power analysis (section 17.2) and statistical analysis (section 17.3) sections are described separately for these two goals.

For the qualitative sub-study analysis, data from debrief session conducted with SPs following each clinic visits will be transcribed and translated into English by study staff and spot checked by the co-PIs for transcription accuracy by bilingual

PROTOCOL TITLE: Standardized Patients to Address Intersectional Stigma  
VERSION DATE: 07/23/2019

study staff. Co-PIs will oversee analysis by study staff including coding of transcripts and identification and interpretation of emergent themes.

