#### 17.2 Power Analysis:

**Stigma Quantification:** The primary objective of this pilot study is to estimate the extent to which stigma towards PLWH (HIV stigma) and towards MSM (homophobia) contribute to the deterioration of healthcare quality relative to straight people without HIV. A total sample size of 160 standardized patient (SP) interactions would provide 80% power (alpha=0.05) to detect a minimum effect size of 0.18 standard deviation. This calculation is conservative in that it does not account for blocked randomization of the SP cases within practices, which will lend additional power to each comparison. Two-sided tests will be needed to detect differences across the four case scenarios in order to separately quantify HIV, sexual, and intersectional stigma, for which the same assumptions will provide the same amount of power to identify a minimum effect size of 0.17 standard deviation between any 2 pairwise comparisons of scenarios. As recruitment will take place at the clinic level, the number of participants that will be needed to be recruited to the study will depend on estimates of the average numbers of eligible providers that our team can reasonably expect to recruit at each clinic. Preliminary data suggest that clinics in our study region employ an average of 5 eligible providers, of whom we conservatively expect to recruit 70% or 3.5 per clinic. Each provider will receive 3 unannounced visits from a standardized patient, yielding a final estimated pool of 56 providers for this study.

**Preliminary intervention effects:** A secondary goal of the RCT is to estimate the preliminary effect of the intervention on quality of care index observed by SPs. Though this is only a secondary goal, we determine that it is plausible that the target enrollment of 20 clinics randomly allocated to treatment and control in a 1:1 manner could yield sufficient power to detect reasonably small effects on the primary outcome measure. That is, with an alpha level of 0.05 for a one-sided test, an intra-cluster coefficient of 0.07, and a baseline prevalence of standardized quality of care index (with mean of 0 and standard deviation of 1), a sample size of 160 SP clinic visits (8 visits per clinic on average) would provide 80% power to detect a reduction in EOC scores due to the intervention as small as 0.17 standard deviations.

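### Section 17.3 labels β3 as the stigma from having both attributes, but β3 is only the excess over additivity; the total dual-status gap, β1+β2+β3, is never specified for the stigma model

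*Combined protocol and SAP*

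**What the plan says.** The stigma model in section 17.3 has an HIV indicator (β1), an MSM indicator (β2), their product (β3), and fixed effects for facility and SP. The paragraph gives β3 two meanings.

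- **Before the equation**, the aim is to find a loss of care quality in dual-status visits that goes "beyond the simple sum or product of the erosion experienced with only one of the attributes". This is an interaction.
- **After the equation**, β1 and β2 are read as HIV stigma and MSM stigma, and β3 is read as "the estimate of stigma due to the presence of both HIV and MSM status".

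Other sections describe dual-status stigma as a gap between scenarios.

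- Section 3.1 takes the straight, HIV-uninfected man as the referent.
- Section 17.1 includes intersectional stigma, meaning stigma towards patients with both attributes, in the primary goal. It states: "Stigma is quantified as the difference in the mean healthcare quality index across the four case scenarios".
- Section 17.2 says HIV, sexual and intersectional stigma are to be quantified separately, and gives a detectable effect of 0.17 SD "between any 2 pairwise comparisons of scenarios".
- The intervention model at the end of section 17.3 has a separate dummy for the dual-status script, and interprets its interaction with treatment against the HIV-/MSM- script.

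**The concern.** In this coding β1 and β2 are each a gap against the referent. A reader who follows the sentence that interprets the coefficients will take β3 as the matching gap for a patient with both attributes. It is not: that gap is β1+β2+β3, and section 17.3 does not name this combination for the stigma model.

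Intersectional stigma is in the study title and in the primary goal of section 17.1. Under its label, β3 could understate what dual-status patients experience, or show it with the opposite sign. β3 is also estimated less precisely than a pairwise gap, and section 17.2 gives no detectable effect for it.

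**Working it through.** **Inputs.** 160 visits, 80% power, alpha 0.05 and two-sided tests are from the stigma paragraph of section 17.2. The index SD of 1 and the ICC of 0.07 are from its intervention paragraph. An equal split of 40 visits per scenario (160/4) is an assumption; section 12.1 plans only to balance the scenarios.

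**Step 1: the plan's own figures.** The detectable difference is (1.960 + 0.842) × SE = 2.802 × SE.

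- Pairwise, 40 v 40: SE = √(2/40) = 0.224, giving 0.63 SD. The plan states 0.17 SD. Power at 0.17 SD is about 12%.
- One attribute against the other half of the visits, 80 v 80: SE = √(2/80) = 0.158, giving 0.44 SD. The plan states 0.18 SD for its overall comparison.

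Neither stated figure reproduces. That is a separate matter, and this point does not depend on it.

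**Step 2: what each coefficient is.** Let μ11 be the mean index for HIV+/MSM+, μ10 for HIV+ only, μ01 for MSM only and μ00 for the referent. Then:

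- β1 = μ10 − μ00
- β2 = μ01 − μ00
- β3 = μ11 − μ10 − μ01 + μ00, a four-cell contrast
- dual-status gap = μ11 − μ00 = β1 + β2 + β3, a pairwise contrast

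The definition in 17.1 and the power basis in 17.2 correspond to the last line. The stated aim in 17.3 corresponds to β3, but only for the sum: a product term in a linear model of the index does not test departure from a product of effects.

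**Step 3: precision of each** (SD 1, 40 per scenario, fixed effects and blocking ignored).

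- Total gap: SE = √(2/40) = 0.224; detectable 2.802 × 0.224 = 0.63 SD
- β3: SE = √(4/40) = 0.316; detectable 2.802 × 0.316 = 0.89 SD

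**Step 4: illustration.** The effect sizes are assumed, with β1 = β2 = −0.5 SD throughout.

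| β3 | Total gap | Power for total gap | Rejection rate for β3 |
|---|---|---|---|
| 0 | −1.0 | 99.4% | 5.0% |
| +0.2 | −0.8 | 94.7% | 9.7% |
| +0.5 | −0.5 | 60.9% | 35.3% |
| −0.3 | −1.3 | >99.9% | 15.8% |

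In the first row a 1 SD gap goes with a β3 of zero. In the second and third, care is worse for dual-status patients than for the referent while β3 is positive.

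**Step 5: check with fixed effects.** 2,000 trials were simulated with 20 clinics × 8 visits (two of each script per clinic), 8 SPs, ICC 0.07, clinic and SP fixed effects, and true values −0.5, −0.5 and 0. The total gap averaged −1.00 and was rejected in 99.3% of runs. β3 averaged +0.01 and was rejected in 6.0%. The empirical SDs were 0.228 and 0.316, close to Step 3, so at this ICC the fixed effects change little.

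**The case against.** The strongest reply is that the aim stated before the equation governs how β3 is read. That aim is excess over the sum, β3 is the right coefficient for it on the additive scale, and the label can be taken as shorthand for the extra stigma that arises when the attributes occur together. The abbreviation list also defines the relative excess risk due to interaction, which suggests that an interaction was intended. On that reading a β3 of zero or above is a correct finding of no excess, or of sub-additivity. This stands: the regression and the interaction test are sound.

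A reader might infer that the plan will report large dual-status stigma as zero or with the wrong sign. The documents do not support that. β1 and β2 come from the same fit, and sections 17.1 and 17.2 call for scenario mean differences and pairwise comparisons, all of which would show the total gap.

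A reader might also infer that the two models in section 17.3 contradict each other. They need not: one asks about excess over the sum, the other how training changes each scenario's gap from the referent, and the second states its contrast explicitly.

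Finally, sections 1.1 and 2.1 say that the preparatory phase is complete and that baseline stigma results have been shared with the advisory boards, which limits the consequence for the training analysis. Section 17.1 nevertheless still names stigma quantification as the primary goal.

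What the reply does not remove is that the plan holds two meanings of dual-status stigma, attaches the label for one to the coefficient for the other, and never writes down the total contrast.

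**Conclusion.** The point holds as a fault in the label and a missing contrast, not in the model, design or data. β3 is the departure from additivity. The quantity that 17.1 defines and 17.2 powers is β1+β2+β3. The algebra holds for any effect sizes.

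The misreporting described is a risk of one reading of the label. How large it would be depends on the true single-attribute effects, which the documents do not give. The difference in precision is a factor of √2: about 0.63 SD detectable for the total gap against 0.89 SD for β3, under the assumptions in Step 3. Whether β3 would come out null cannot be said without a true interaction, and a null would be correct if there is no excess.

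Because this concerns the interpretation of a primary-goal quantity and costs almost nothing to correct, it should be corrected.

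**What to change.** In section 17.3:

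- Relabel β3 as the additive-scale interaction, that is, intersectional stigma in excess of the sum of the HIV and MSM effects.
- Drop the reference to a product, which this linear model does not test.
- Pre-specify β1+β2+β3, with its confidence interval, as dual-status stigma against the HIV-/MSM- referent. The intervention model already uses that contrast and needs no change on this point.

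In section 17.2, state the detectable effect separately for the total gap and for β3, with the visits per scenario and the SD assumed.

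The cost is a few sentences in the plan and one linear-combination command in the analysis code. No new data or design change is needed.

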### 3.0 Study Endpoints/Events/Outcomes

#### 3.1 Primary Endpoint/Event/Outcome

Our primary endpoint of the RCT phase of the study will be the quality of healthcare received by SPs in each clinical encounter with an enrolled provider. As a measure of the quality of healthcare provided in each interaction between physicians and standardized patients, we will create an index using 38 items from the structured post-interaction survey questionnaire administered to SPs following each unannounced visit. Individual items will be combined into a global index,  $\bar{s}_i$ , which is calculated as a weighted average of all 38 items, for which weights are calculated as the sum of its row entries in the inverted covariance matrix as follows:

$$\bar{s}_i = (1' \hat{\Sigma}^{-1} 1)^{-1} (1' \hat{\Sigma}^{-1} y_i)$$

where 1 is a column vector of 1s,  $\hat{\Sigma}^{-1}$  is the inverted covariance matrix, and  $y_i$  is a column vector of all items for individual  $i$ .

Using the analysis approach presented in section 17.3, we will estimate the impact of the intervention on the extent to stigma faced by SPs when presenting as MSM or HIV infected patients relative to the "standard" care experienced by the referent case scenarios of a straight, HIV uninfected man.

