## **16.0 Potential Benefits to Participants**

Provider participants randomized to the treatment arm will benefit from the opportunity to take part in the stigma reduction intervention. Those randomized to the control arm will not access this benefit. However they may gain indirect benefits in the form of contributing the development and evaluation of an intervention to reduce the incidence of stigmatizing and discriminatory behavior towards PLHA and MSM in Chinese medical settings. If found effective, the intervention developed in the course of this study may be adopted by provincial policy makers (our co-investigators at the GDCDC) and incorporated into routinized clinical training throughout the provincial network of DV practices. The model for measuring and addressing enacted healthcare stigma developed in the course of this study will also be documented and disseminated with the intention for it to be replicated in other settings, particularly in low/middle-income settings that bear the greatest burden of HIV worldwide and where stigma is most severe.

SPs taking part in our qualitative sub-study may benefit from the interviews by having an opportunity to share their personal experiences with the study team or air any grievances about study conduct.

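### Section 17.3 labels the overall-quality coefficient the main training effect, although the plan's stated goal is the change in the stigma gap; the 0.17 SD power claim in 17.2 fits neither

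*Combined protocol and SAP*

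**What the plan says.** Throughout, beta_1 means the coefficient of clinic assignment in the intervention model of 17.3, not the HIV coefficient in the stigma-quantification model.

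Places that make the gap between scripts the target:
- Section 3.1: "we will estimate the impact of the intervention on the extent to stigma faced by SPs when presenting as MSM or HIV infected patients", judged against the straight, HIV-uninfected script.
- Section 17.3, after the two-stage model: "the goal is to estimate the effect of the training on" enacted stigma, and "we are primarily concerned with observing how the training affects the difference in the quality of care received by patients presenting as MSM" or HIV-positive compared with those who do not. The same sentence places this above the overall level of quality. The coefficients are alpha_11 to alpha_13.

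Places that make the overall level the target:
- Section 17.3, opening of the intervention analysis: "We will estimate the main intention-to-treat (ITT) impact of the training intervention using the Ordinary Least Squares (OLS) regression". It names beta_1 as the coefficient of interest, "which captures the ITT effect of training on the quality of care".
- Section 17.1: the secondary goal is to "assess the preliminary effect of the intervention on healthcare quality by comparing the same healthcare quality index across treatment arms".

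Section 17.2 mixes the two. It starts from the quality index and uses arm-comparison inputs (20 clinics 1:1, ICC 0.07, 160 visits, SD 1, one-sided 5%), then concludes that this "would provide 80% power to detect a reduction in EOC scores due to the intervention as small as 0.17 standard deviations". EOC is listed as erosion of care, and 17.3 uses erosion for the loss of care under disclosed scripts, so the natural reading is a gap.

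No section gives a testing order, a multiplicity rule for the three gap coefficients, or a power figure of their own.

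**The concern.** The study's purpose is to reduce enacted stigma, and 17.1 defines stigma as a difference between scripts. The coefficient carrying the main label does not measure that difference. Part of the course (section 1.1) is general: STI management, history taking, shared decision making. Equal improvement for every kind of patient is therefore a possible result. It would produce a positive main effect with stigma unchanged.

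The label and the power statement are what readers of the results, and planners of the full-scale trial, will look to. If they attach to beta_1, a general quality gain may be reported under a stigma-reduction title. The 0.17 SD figure would also suggest a precision for the gap that the design does not have.

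**Working it through.** **Inputs (17.2):** 20 clinics 1:1, 8 visits each (160), ICC 0.07, SD 1, one-sided alpha 0.05, 80% power. **Assumed:** even split over four scripts (20 visits per script per arm, balanced within clinic), a single clinic-level random effect, no baseline adjustment. Multiplier: 1.645 + 0.842 = 2.487.

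**1. The plan's 0.17 SD.** Design effect = 1 + 7 × 0.07 = 1.49.
- SE(beta_1) = sqrt(4 × 1.49/160) = 0.193; detectable effect = 2.487 × 0.193 = **0.48 SD** (0.50 with t on 18 df).
- Power at 0.17 SD is 22%.
- Other readings also miss 0.17: two-sided 0.54; clustering ignored 0.39; 320 visits over both rounds 0.40, or 0.28 without clustering.
- Reaching 0.17 would need covariates explaining 1 − (0.17/0.48)² ≈ 87% of the variance, or 856 × 1.49 ≈ 1,275 visits.

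**2. The gap contrasts.** Clinic effects cancel within clinic.
- Each of alpha_11 to alpha_13: SE = sqrt(0.93 × 4/20) = 0.431; detectable effect = 2.487 × 0.431 = **1.07 SD**. Power at 0.17 SD is about 11%.
- One pooled gap (three disclosed scripts against the referent): SE = sqrt(2 × 0.93 × (1/60 + 1/20)) = 0.352; detectable effect = **0.88 SD**.

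**3. What beta_1 measures.** With balanced scripts, and script main effects in the gap model, beta_1 = alpha_1 + (alpha_11 + alpha_12 + alpha_13)/4.
- A uniform gain of 0.30 with no gap change gives 0.30.
- If gaps of −0.3, −0.3 and −0.6 SD (illustrative values) close completely with no gain for the referent, the result is (0.3 + 0.3 + 0.6)/4 = 0.30.

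The same beta_1 arises from opposite stigma results.

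**4. Simulation of a uniform 0.48 SD gain with unchanged gaps** (no SP effects or baseline covariate; script main effects handled).

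| Analysis | beta_1 significant (one-sided 5%) | Gap significant |
|---|---|---|
| Clinic summaries, t on 18 df, 20,000 trials | 77% | pooled gap 5% (one-sided) |
| OLS, clinic-clustered SE, 3,000 trials | 79% | each alpha about 5% (two-sided) |

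With the illustrative gaps fully closed and no referent gain, beta_1 averaged 0.31 and was significant in 46%.

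**5. The printed gap equation.** Its covariate vector holds SP effects only; script main effects appear in the overall model but not here. Without them, each interaction coefficient is the script difference within the treated arm, not the difference between arms. Simulated with no training effect and the same illustrative gaps, the printed form returned −0.30, −0.29 and −0.60: the existing stigma level, not a change in it.

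**The case against.** The strongest reply is that the text already protects the reader. Section 17.3 describes beta_1 as an effect on quality of care, then says the concern is the gap and gives it a separate model. Main may only distinguish ITT from the two-stage estimate that follows. The study is a pilot and the intervention effect a secondary, preliminary goal. The gap is also the weaker test: when a 0.5 SD gain is confined to the disclosed scripts, beta_1 is significant in 59% of simulated trials and the pooled gap in 39%. A pooled contrast would merge HIV, MSM and intersectional stigma, which the plan keeps apart.

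Much of this stands. The gap has verbal priority, pooling should be optional, and leading with the gap costs power. It does not remove the conflict. Sections 17.1 and 17.2 still frame the intervention question as an arm comparison, 17.2 still attaches a figure to erosion of care that its inputs do not support, and beta_1's greater power does not make it specific to stigma.

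Three stronger readings are tempting but unsupported:
- A reader might infer two unranked tests, either of which decides success. Section 17.3 does rank them in words, and there is no pass/fail rule; "If found effective, the intervention developed in the course of this study may be adopted by provincial policy makers" stands in the benefits text and sets no criterion.
- A reader might infer that a uniform gain is the likely result. The course also covers work with marginalised groups, and nothing shows which effect will dominate.
- A reader might set the chance of at least one false positive among beta_1 and the three gap coefficients, about 17%, against the stated 5%. Section 17.2 states that alpha for one comparison and claims no familywise control.

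**Conclusion.** The concern holds as a conflict between the plan's stated goal and its labels, goal statement and power claim. The goal is the change in the script gap; the main label, 17.1 and the inputs of 17.2 belong to overall quality. beta_1 is a valid test of overall quality but cannot show that stigma fell.

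The 0.17 SD claim holds for neither contrast: about 0.48 SD for beta_1, 1.07 SD for each gap coefficient, 0.88 SD for a pooled gap. These figures rest on an even script split, a common ICC of 0.07 and no baseline adjustment. Adjustment would improve precision by an amount the documents do not allow one to calculate, but reaching 0.17 SD even for beta_1 would need about 87% of the variance explained.

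The documents do not support saying that the plan lacks any priority between the contrasts, or that following it would declare stigma reduced on beta_1 alone. The change is worth making before analysis, in proportion to a pilot.

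**What to change.** - **17.1 and 17.3:** name the training-by-script gap as the leading intervention estimand, consistent with 3.1. Keep alpha_11 to alpha_13 separate, and either state a multiplicity rule or label them exploratory. A pooled contrast is optional.
- **17.3, gap model:** add script main effects.
- **17.3, overall model:** drop the main label, describe beta_1 as overall quality of care (supportive), and state that no stigma-reduction claim rests on it.
- **17.2:** replace the EOC statement with the detectable effect for each contrast at the plan's inputs: about 0.48 SD (beta_1), 1.07 SD (each gap coefficient) and, if used, 0.88 SD (pooled gap), with the assumptions stated.

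Cost: text edits and three model terms; no new visits or data. The drawback is a much less favourable precision statement for the leading contrast. A multiplicity rule adds to it: for two-sided tests the detectable gap rises from 1.21 SD to 1.40 SD with Bonferroni over three. That is acceptable where the intervention effect is declared preliminary and secondary, and it gives the planned full-scale trial an honest starting point.

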## 11.0 Number of Participants

### 11.1 *Number of Participants to be Consented:*

To demonstrate the preliminary effectiveness of the intervention we recruited approximately 20 facilities within which an estimated 8 eligible providers work. For the baseline visits a total of 160 unannounced SP visits were made, or about 8 visits per clinic. Given the nature of patient intake procedures at outpatients facilities of the type that our SPs will visit, we were unable to control which of the consented providers in a given facility consented to SP visits. It is therefore possible that some consented providers in these clinics will never receive an unannounced SP visit, while others may receive multiple visits.

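### The three intervention models adjust for each doctor's own baseline mean but give no rule for a doctor without one, so those follow-up visits would drop out; separately, the provider counts in 11.1 and 17.2 disagree

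*Combined protocol and SAP*

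**What the plan says.** In the combined protocol and SAP, section 17.3 specifies the ITT regression and states "We control for the average quality index from all SP interaction with doctor" d at baseline. The same baseline mean appears in both stages of the two-stage least squares model and in the treatment-by-script model. The last of these targets what 17.3 treats as the main question: "we are primarily concerned with observing how the training affects the difference in the quality of care received" by patients presenting as MSM or HIV-positive compared with those who do not.

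Section 11.1 describes how visits reached doctors: "we were unable to control which of the consented providers in a given facility consented to SP visits". It continues: "It is therefore possible that some consented providers in these clinics will never receive an unannounced SP visit, while others may receive multiple visits". No section says what to do when a doctor has no baseline mean. The only text on missing values, in 17.4, concerns checks at data entry.

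On numbers, 11.1 reports "approximately 20 facilities within which an estimated 8 eligible providers work" and adds: "For the baseline visits a total of 160 unannounced SP visits were made, or about 8 visits per clinic". Section 17.2 takes an average of 5 eligible providers per clinic, "of whom we conservatively expect to recruit 70% or 3.5 per clinic", and then states: "Each provider will receive 3 unannounced visits from a standardized patient, yielding a final estimated pool of 56 providers". Its next paragraph uses 20 clinics and 160 visits.

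**The concern.** A doctor's baseline mean exists only if an SP saw that doctor at baseline. Intake decides which doctor an SP meets, so a doctor missed in the first round can be met in the second. OLS and two-stage least squares routines delete rows with a missing covariate. The plan does not call for deletion; it follows from fitting the equations as they stand.

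The analysis labelled ITT would then leave out some follow-up visits made in randomised clinics and would describe only doctors seen in both rounds. With 20 clinics and about 160 follow-up visits, there is little precision to spare, least of all for the script interaction.

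The size of the loss depends on how many consenting doctors each clinic has. That is the quantity on which 11.1 and 17.2 disagree.

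**Working it through.** **Provider counts.** The plan's 56 does not follow from its stated inputs.

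- 5 eligible × 70% = 3.5 per clinic; 20 clinics × 3.5 = 70 providers, not 56.
- 56 / 3.5 = 16 clinics. One route to it: 160 / (3.5 × 3) = 15.2, rounded up to 16, and 16 × 3.5 = 56.
- At 3 visits each, 56 providers need 168 visits and 70 need 210; the plan has 160.
- 160 / 70 = 2.3 visits per provider, not 3.
- Eligible providers per clinic are 5 in 17.2 and 8 in 11.1, reading the 8 as per facility.
- A fixed 3 visits per provider cannot stand beside 11.1's statement that some providers may receive none.

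**Share of follow-up visits without a doctor baseline.** Assume k consenting doctors per clinic, 8 visits per clinic in each round, independent assignment and no turnover. With equal chances, a follow-up visit reaches a doctor unseen at baseline with probability (1 − 1/k)^8. With uneven caseloads, represented by a flat Dirichlet distribution of patient shares (assumed), the probability is k(k − 1) / [(k + 8)(k + 7)].

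| k | Source | Equal chances | Of 160 visits | Uneven caseloads |
|---|---|---|---|---|
| 2.8 | 56 / 20 | 0.029 | about 5 | 0.048 |
| 3.5 | 17.2 | 0.068 | about 11 | 0.072 |
| 5.6 | 70% of 11.1's 8 | 0.207 | about 33 | 0.150 |

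If every provider had at least one baseline visit, as 17.2's 3 visits each would imply, the share is 0.

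**Effect on standard errors.** The simulation used 20 clinics allocated 1:1, 8 visits per clinic per round, and clinic variance 0.07 with total variance 1 (17.2's intra-cluster coefficient). Assumed inputs were doctor variance of 0.05, 0.15 or 0.30, a script gap of −0.4 SD and no training effect. SP and script fixed effects were in every model, with 4,000 trials per setting. The plan as written was compared with the doctor mean plus missing indicator fitted to all visits. Results below are for equal caseloads with scripts and SPs balanced within clinic, in order of doctor variance.

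| k | Model | As written | All visits, indicator | Ratio |
|---|---|---|---|---|
| 3.5 | ITT | 0.195, 0.195, 0.189 | 0.191, 0.190, 0.186 | 1.02, 1.03, 1.02 |
| 3.5 | Interaction | 0.461, 0.447, 0.410 | 0.444, 0.430, 0.395 | 1.04, 1.04, 1.04 |
| 5.6 | ITT | 0.210, 0.203, 0.197 | 0.191, 0.187, 0.185 | 1.10, 1.09, 1.06 |
| 5.6 | Interaction | 0.508, 0.501, 0.466 | 0.444, 0.439, 0.415 | 1.14, 1.14, 1.12 |

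A separate simulation gave +1–2% (ITT) and +3–5% (interaction) at 3.5, and +7–9% and +12–14% at 5.6, with no bias under the null. Together the ranges are about +1–3% and +3–5% at 3.5, and +6–10% and +12–14% at 5.6. With uneven caseloads at 5.6 they fall to +5–8% and +7–10%. The two-stage least squares coefficient is the ITT estimate divided by the first stage on the same rows, so it loses the same visits.

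**Which replacement.** Using the clinic baseline mean also keeps every visit. However, at k = 3.5 with doctor variance 0.30 its ITT standard error was 0.191, against 0.189 as written. The doctor mean plus indicator was never less precise than the plan as written in the settings examined.

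**The case against.** The event is inferred. No section reports a doctor seen at follow-up but not at baseline, and a doctor visited in neither round costs the models nothing. The sentence in 11.1 about lack of control is also awkwardly worded, and taking it to mean which doctor was seen is a reading, though the natural one. This stands, and it is why the size can only be given as a range starting at 0%.

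At 17.2's own 3.5 doctors per clinic the harm is small. This stands too. The 5.6 figure combines inputs from two sections, and the simulation variances and script gap are assumptions.

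The intervention effect is called secondary in 17.1 and 17.2, in a pilot. But 3.1 makes the index the RCT-phase primary endpoint and commits to estimating the intervention's effect on stigma. Section 2.4 promises a fuller analysis plan before analyses start; that is a suitable home for the rule but does not supply it.

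On the counts, 56 is a planning estimate in a paragraph that names no number of clinics, and none of the 17.3 models uses it. The mismatch is largely clerical, but the text does not reconcile it.

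Two stronger readings are tempting. Because consent followed randomisation and only treatment-arm providers were asked to join the workshop (22.1), a reader might infer that the missing share differs by arm and biases the ITT estimate. The documents give no consent counts by arm, and 22.1 has consent to the survey and SP visits sought in both arms. A difference cannot be excluded, but none is shown, and no choice of baseline covariate would remove such selection. A reader might also project a larger loss by supposing that all 8 eligible providers consented; 12.1 and 22.3 describe providers who declined.

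**Conclusion.** The concern holds as a gap in the specification with a modest cost. Fitted as written, all three models would drop follow-up visits to any doctor without a baseline visit, and the documents do not say how many such visits there are. Under random assignment of 8 visits per clinic, the expected loss is about 7% at 3.5 doctors per clinic and about 21% at 5.6 (15% with uneven caseloads). The standard-error cost is slight in the first case and noticeable in the second, chiefly for the script interaction. The harm is lost precision and an estimate confined to doctors seen in both rounds. It should not be read as evidence of bias. The count discrepancy is a separate and definite error: 70 providers, not 56, follow from 20 clinics at 3.5 each.

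**What to change.** Add a rule to 17.3, or to the analysis plan promised in 2.4, before follow-up data are analysed: every follow-up visit stays in the ITT, two-stage least squares and treatment-by-script models. As the main analysis, keep the doctor baseline mean, set missing values to a constant and add a missing-baseline indicator. As a sensitivity analysis, use the clinic baseline mean instead. Report by arm the numbers of follow-up visits and doctors without a doctor-level baseline; those counts would also show whether the arms differ. The cost is one sentence and one model term, with no new data, and the simulated standard errors above already include that term.

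Separately, make 11.1 and 17.2 agree on clinics, eligible and consented providers per clinic, total providers, visits per provider and the 160 visits. With 20 clinics at 3.5 that means 70 providers and about 2.3 visits each. Settle whether 5 or 8 eligible providers applies, and reconcile the fixed 3 visits per provider with the statement that some may receive none.
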